Which methods will this study include? (check all that apply)

- Descriptive
- Qualitative
- Quantitative
- Formative
- Other, specify:
- Oral History
- Experimental/Control Design
- Ethnographic
- Longitudinal

Estimated Study Duration

Please indicate the estimated length of research study:
Between 1 and 2 years

Publication of Results

Please identify all methods in which you may publicly disseminate the results of your study (academic journal, academic conference, a thesis or dissertation for one of your students, etc.).

- Academic journal
- Academic conference paper
- Public poster session
- Book or chapter
- Thesis
- Dissertation
- Class project
- Other:

PROTOCOL SUMMARY

Instructions:

Use non-professional language and address each part separately to describe your protocol. Attaching sections of a grant application or proposal is not an acceptable substitute. Provide sufficient information for effective review by all members of the IRB, including non-specialists. Define all abbreviations and terms that are not part of common language.

Describe the objective(s) of the proposed research:

Describe why this research project will be carried out. Clearly state the overall objectives, specific aims, hypotheses (research questions), and rationale for performing the study.

The overall objective of this study is to explore different ways to accelerate learning to improve memory performance.

The first aim of this study is to investigate the effects of transcranial Direct Current Stimulation (tDCS) stimulating the greater occipital nerve (more specifically the C2 area) during a verbal paired-associate learning task and to determine if tDCS targeting the C2 may be used as a way to enhance brain plasticity during an associative memory task to accelerate learning and to optimize associative memory performance. We hypothesize that participants who received real tDCS will have a better associative memory performance compared to participants who received sham tDCS.

The second aim is to examine whether repeated retrieval practice can accelerate learning and enhance associative memory performance. By using two versions of the verbal paired-associate learning task, we want to investigate the influence of repeated studying and repeated retrieval practice on associative memory performance. We hypothesize that participants with repeated retrieval practice will have a better associative memory performance compared to participants without repeated retrieval practice.

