Previous research has also emphasized the importance of repeated learning and repeated retrieval practice as a way to accelerate learning and enhance associative memory performance (Karpicke and Roediger, 2008). Therefore, in this study we will also examine the effect of repeated learning and repeated retrieval practice on associative memory performance by using two versions of an associative memory task

What information do you expect to obtain and how will the obtained knowledge be applied:

To investigate the effects of tDCS on associative memory performance, we will measure associative memory performance in a group that receives active tDCS and a group that receives sham tDCS. To examine the effect of repeated learning and repeated retrieval practice on long-term memory retrieval, we will use two versions of an associative memory task. Assessments will be done immediately after the learning phase as well as one week after to measure possible (long-term) effects on associative memory performance.

Associative memory performance will be measured using a computerized verbal paired-associate learning task, which includes Swahili-English vocabulary learning. We will base our task on an experiment published in Science by Karpicke and Roediger (2014) where all information is provided to conduct the two versions of the Swahili-English vocabulary learning test.

The knowledge gained from this study will provide evidence as to whether or not tDCS is possible in accelerating learning and in improving associative memory and whether repeated testing can enhance associative memory.

Number of Participants

Please indicate the maximum number of participants that will be involved in the research project at UTD affiliated sites:
 40 healthy subjects will be enrolled (consented) in the study

Will participants from non-UTD affiliated site be included?

- Yes No

If yes, please indicate how many participants are anticipated at each site.

Characteristics of Participants

To which of the following categories do the participants in this research belong?

- | | |
|--|---|
|  Adults |  UTD Students/Staff |
|  Babies and Toddlers (0-3) |  Children in Daycare |
|  Young Children (4-10) |  Children in School |
|  Youth (11-12) |  Teachers or Staff in Schools |

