While the real or sham tDCS stimulation started, the “Learning period” of the computerized vocabulary paired-associate learning task will start which consists of 4 blocks (Karpicke and Roediger, 2008), each consisting of a study phase and a test phase. The 4 blocks are spread with a 30 second distractor task between the blocks. During the study phase participants will study 40 successively presented Swahili-English vocabulary pairs comprising common day-to-day words (e.g. Swahili: bustani, English: garden). The word pairs will be presented one below the other in the middle of the computer screen for 5 seconds. For each word pair the Swahili words will be correct transliterations in Roman alphabet of the English words. Participants will be instructed to read and remember the word pairs. The study phase will be followed by a test phase with a cued-recall test: Swahili cue words will be presented successively and participants will have to type-in the English translation during up to 8 seconds presentation time of the Swahili word and to press the return key at the end of the entry. The return key will stop the entry time-window and start the feedback time-window, where the computer program will display the correct English translation of the Swahili word for 1 second below the entry field. In cases when participants do not provide an entry, the computer program will stop the entry time-window after 8 seconds automatically and display the feedback. The second version of the computerized vocabulary paired-associate learning task only differs in the testing phase of the task. Recalled word pairs will be dropped from further testing but studied in each subsequent study period in the second version.

To allocate participants in the different group and test groups in a fair way, participants will be assigned randomly to one of four groups. One group will receive real tDCS paired with version 1 of the computerized vocabulary paired-associate learning task, the second group will get real tDCS paired with version 2 of the computerized vocabulary paired-associate learning task, the third group will receive sham tDCS paired with version 1 of the computerized vocabulary paired-associate learning task and the fourth group will get sham tDCS paired with version 2 of the computerized

vocabulary paired-associate learning task.

After the tDCS procedure paired with the memory test, participants will need to fill out a tDCS questionnaire.

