Visit 2: i.e. 1 week after the first visit – Approximately 10 minutes: At the lab, the participants will start the test phase of the vocabulary paired-associate learning task. This is identical to the test phase from the learning period, i.e. all participants performed a cued-recall test with feedback, but did not restudy the word pairs.

Will archival data be used?

Yes No

If yes, please continue

Describe the records: medical, educational, employment existing data set, or pathological specimens:

Do you have permission to access the records or specimens?

Yes, these sources are publicly available. Identify the source (*e.g., database name, website address, etc.*)

Yes, other. Identify the source and describe how you have permissible access to the records.

No

Number of records or specimens to be used:

Will the records you receive be stripped of all identifiers that would make it possible for you to identify a participant?

Yes

No

Describe the identifying information to which you will have access to prior to recording data:

Describe the identifying information you will record:

Confirm that the data/specimens you wish to review already exist.

The data set exists

The data set does not already exist

Confirm that you will not have access to, or create a link, which would make it possible to identify participants.

I will not have access to, or create a link.

I will have access to a link, explain:

If this record or specimen became publicly available, could it have negative psychological, physical, economic, sociological or legal consequences for the participant from which it originated?

Yes No

If yes, describe the potential negative consequences.

RISK/BENEFIT ASSESSMENT

A reasonable person would consider it to be important to know the risk of harm or discomfort when deciding whether to participate in the research project.

Potential Risks

Are there risks of physical harm or discomfort associated with the research?

Yes No

If yes, describe: - The most common side-effect of neurostimulation is temporally local redness of the skin direct under the electrode. This disappears within 1 hour.

- Itching at the site of the electrode, passing within the hour

- Slight feeling of dizziness when starting the stimulation occurs in a small number of participants. This takes only a few seconds and does not affect balance after stimulation

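### Does the 1-second answer display after every learning-period test undermine the Aim 2 comparison of the two task versions?

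*Protocol*

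**What the plan says.** The second aim, in the protocol's objectives section, is tested by comparing two versions of the Swahili-English task: "We hypothesize that participants with repeated retrieval practice will have a better associative memory performance compared to participants without repeated retrieval practice". The section on expected information puts the conclusion to be drawn more broadly, as "whether repeated testing can enhance associative memory".

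The Visit 1 description sets out the task. There are four blocks, each with a study phase and a test phase on 40 pairs. In the study phase, "The word pairs will be presented one below the other in the middle of the computer screen for 5 seconds". In the test phase the participant types the English word, and the return key opens a feedback window, "where the computer program will display the correct English translation of the Swahili word for 1 second below the entry field". If nothing is entered, "the computer program will stop the entry time-window after 8 seconds automatically and display the feedback". Feedback thus follows every test trial.

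The versions differ only in testing: "Recalled word pairs will be dropped from further testing but studied in each subsequent study period in the second version". Participants are randomised to four groups, real or sham stimulation by version 1 or 2. The Visit 2 section says of the one-week test: "This is identical to the test phase from the learning period, i.e. all participants performed a cued-recall test with feedback".

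**The concern.** A pair dropped from testing in version 2 loses two things at once: the later attempts to retrieve it and the later displays of its translation. Version 1 keeps both. Nothing in the protocol gives dropped pairs a matching display, and no group receives matched feedback across versions. The two quantities differ between versions by exactly the same count, so no model fitted to the version contrast can separate them.

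If version 1 does better at one week, a reader of the second aim would credit retrieval practice, although part of the gain could come from seeing the answer more often. Because the task program fixes this, an analysis plan could not repair it later. The interpretation of Aim 2 is at stake. The real-versus-sham comparison within a version is not, because both arms follow the same feedback rule.

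**Working it through.** **Inputs, all from the Visit 1 description:** 40 pairs; 4 blocks; 5 s of study per pair per block in both versions; 1 s of feedback per test trial; in version 2, no further tests after the first recall, but study continues. The protocol states no exposure total, so there is no figure of its own to reproduce.

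**Per pair.** Study exposure is 4 × 5 = 20 s in both versions. Version 1 adds 4 × 1 = 4 s of feedback, giving 24 s. In version 2 a pair first recalled in block k is tested k times, giving 20 + k s; a pair never recalled is tested four times.

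| First recalled in block | Extra tests in version 1 | Extra answer displays in version 1 | Version 1 (s) | Version 2 (s) | Excess |
|---|---|---|---|---|---|
| 1 | 3 | 3 | 24 | 21 | 3/21 = 14.3% |
| 2 | 2 | 2 | 24 | 22 | 2/22 = 9.1% |
| 3 | 1 | 1 | 24 | 23 | 1/23 = 4.3% |
| 4 or never | 0 | 0 | 24 | 24 | 0% |

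The second and third columns are identical, which confirms the one-to-one link.

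**Per list, with no assumption about recall.** Version 1 gives 40 × 24 = 960 s. Version 2 lies between 40 × 21 = 840 s and 40 × 24 = 960 s. The excess is 0 to 120 s, at most 120/840 = 14.3%. The upper end requires all 40 pairs to be recalled at the first test, after one 5 s study trial, by participants selected for not knowing Swahili.

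**Per list, with an assumed recall rate.** The protocol gives no rate. Suppose each not-yet-recalled pair is recalled with constant probability h at each test. Version 2 exposure is then 800 + 40 × [1 + (1−h) + (1−h)² + (1−h)³].

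- h = 0.1: 937.6 s; excess 22.4 s, 2.4%
- h = 0.3: 901.3 s; excess 58.7 s, 6.5%
- h = 0.4: 887.0 s; excess 73.0 s, 8.2%
- h = 0.5: 875.0 s; excess 85.0 s, 9.7%
- h = 0.9: 844.4 s; excess 115.6 s, 13.7%

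**Counted as presentations.** Version 1 shows each answer 4 + 4 = 8 times; version 2 shows it 5 to 8 times. The largest excess is 8/5 − 1 = 60%, under the same extreme condition.

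**What the protocol claims.** The aim contrasts participants with and without repeated retrieval practice and says the two task versions will be used to do so. It does not say that retrieval is isolated from feedback. The Visit 1 text describes the feedback openly, and the Visit 2 text names the test as cued recall with feedback. The expected-information section speaks of repeated testing, which is what the versions vary. These statements are compatible.

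**What a task change would do.** Without learning-period feedback, programmed exposure would be 20 s per pair in each version. But each extra version 1 test would still bring a cue on screen for up to 8 s and, on success, the English word typed by the participant, so exposure would still rise with testing. Error correction would disappear from every learning-period test in all four groups, block 4 errors would stand uncorrected until Visit 2, and the Visit 2 test would no longer match the learning-period test. Giving dropped pairs a matched 1 s display in version 2 would bring both versions to 960 s, but would add an answer display to pairs that version 2 otherwise only restudies. Each option trades one feature of the task for another.

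**The case for a change.** The strongest case for acting is that the link is built into the task and can be broken only before data collection. Small in seconds need not mean negligible in effect: a version 1 pair recalled once and later missed gets an immediate correction that its version 2 counterpart does not, and the excess looks larger when presentations rather than seconds are counted. The protocol also uses both retrieval practice and repeated testing for the same contrast, so a reader could take the narrower meaning, and a clarifying phrase would cost little.

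Much of this stands. The two components cannot be separated, and the share of any version effect due to feedback is unknown. But the extra displays fall only on pairs already recalled once and still restudied for 5 s in each later block, so they add new information mainly when such a pair is later failed. The document does not show that feedback would explain a version difference. Adding the words 'with feedback' to the aim would change no procedure, estimate or result; anyone reporting the trial has the task description and can name the contrast accurately.

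**Conclusion.** The observation is correct, but no change to the plan follows. Version 1 adds 3, 2, 1 or 0 retrieval attempts, and equally many 1 s answer displays, for a pair first recalled in block 1, 2, 3 or 4. That is at most 3 s per pair on top of at least 21 s, and 0 to 120 s over the list. These bounds rest only on the protocol's task settings; the 6.5% to 9.7% range rests on assumed recall rates of 30% to 50% per test.

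The version comparison remains a valid randomised estimate of repeated testing with feedback against dropping recalled pairs from testing, and a report should describe it that way. It does not show the effect of retrieval with feedback held constant, and the protocol does not say that it will. Keeping feedback in the task is a fair trade-off: removing it would change the learning conditions in every group, including those used for Aim 1, without making the versions differ in retrieval alone.

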- Very rarely, temporary skin damage may occur under the electrode. This gives a darkening of the skin, which normalizes after a weeks and heals. The size of such etch is a few millimeters. This is harmless, however, with the current that we will handle, this risk is minimal.

On the safety of tDCS in healthy volunteers, in 2005 a well-conducted study published in the Journal of Neurology. There is a group of 103 people total tDCS stimulation given to 2 mA. Outside redness and itching they describe a transient slight improvement in language fluency (pronouncing words) or a transient slight delay in language fluency. The technique is seen as safe.

Are there risks of psychological harm or discomfort associated with the research procedure?

Yes No

If yes, describe:

Are there risks of social harm to the participants associated with the research?

Yes No

If yes, describe:

Are there economic risks associated with the research?

Yes No

If yes, describe:

What is your assessment of the overall risk classification of this research?

Minimal

Greater than Minimal Risk and the study presents the prospect of direct benefit to the participants

Greater than Minimal Risk and the study presents no prospect of direct benefit to the participants, but will likely yield generalizable knowledge about the study question.

Minimizing Risks

How will you minimize risks or discomfort?

Monitor the experiments by professional staff.

Provide opportunities for rest or breaks.

Withdrawal of participant based on specific criteria, explain: : All participants who are terminated from the study will have the reason for their termination documented. Reasons for termination may include: lost-to-follow-up, participant-initiated withdrawal, staff-directed withdrawal, completion of study.

Remind participant of his/her opportunity to stop or withdraw.

Modification of process, explain:

Other, describe:

Potential Benefits

Benefits to participants do NOT include monetary incentives paid in return for participation.

Please describe any direct benefits anticipated for the individual participants in this study:

None

Please describe any potential benefits to society:

Knowledge gained from this study can be used in aging and patient populations, such as patients with Mild Cognitive Impairment or Alzheimer's disease, where memory performance is one of the first aspects to be impacted.

DATA PRIVACY & CONFIDENTIALITY

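### Harms are not systematically asked about after visit 1, so the course of the one listed effect lasting beyond an hour, and any delayed effect, is left to spontaneous report in all groups

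*Protocol*

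**What the plan says.** Under the description of participant activities, visit 1 comprises baseline questionnaires, electrode set-up, and real or sham stimulation during the learning task. It ends with one form: "After the tDCS procedure paired with the memory test, participants will need to fill out a tDCS questionnaire". The protocol does not say what that form asks.

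The second visit is headed "Visit 2: i.e. 1 week after the first visit – Approximately 10 minutes". Its content is the recall test: "all participants performed a cued-recall test with feedback, but did not restudy the word pairs". No symptom question, skin check or repeat of the visit 1 form is described.

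The Potential Risks section lists four physical effects, each with a duration:

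- Redness: "The most common side-effect of neurostimulation is temporally local redness of the skin direct under the electrode. This disappears within 1 hour".
- Itching: "Itching at the site of the electrode, passing within the hour".
- Dizziness when the current starts: "This takes only a few seconds and does not affect balance after stimulation".
- Skin damage under the electrode, described as very rare and temporary: "This gives a darkening of the skin, which normalizes after a weeks and heals".

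Two other places bear on harms. Before signing, participants are asked what they should do if they have symptoms from the stimulation. The Minimizing Risks section says that reasons for termination are documented.

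**The concern.** When harms are asked about is a matter for the protocol. This form itself asks for the frequency and duration of procedures, follow-up included, so the gap is not one that an analysis plan would be expected to fill. The schedule given is a single form soon after the current stops, while the protocol's own risk list contains an effect whose course runs well past that moment. Participants come back to the lab a week later, which is a natural time to ask, and no question is planned.

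At stake is a modest amount of comparable harm data, real against sham, for the week after stimulation. The participants are healthy volunteers with no expected direct benefit. The background also gives a safer procedure as part of the reason for choosing the occipital nerve as target. Spontaneous reports alone do not give a count that can be compared between groups, because participants are not all asked the same question at the same time.

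**Working it through.** The protocol states no figure on this point, so there is none to reproduce. The check sets the assessment schedule against the listed durations and then asks how much a second question could show.

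**1. When the visit 1 form falls.** Task timings from the visit 1 description: 4 blocks, 40 pairs studied for 5 s each, 40 test items of up to 8 s plus 1 s feedback, and 30 s between blocks. For task version 1 the maximum is

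4 × (40 × 5 + 40 × (8 + 1)) + 3 × 30 = 4 × 560 + 90 = 2,330 s, about 38.8 minutes.

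The whole visit is given as 1 hour, so the form is completed soon after stimulation ends.

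**2. What that form could capture**, if it covers side effects (an assumption).

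| Listed effect | Stated duration | Reach of a form straight after stimulation |
|---|---|---|
| Dizziness | seconds, at the start | over by then, can be recalled |
| Redness | within 1 hour | occurrence yes, resolution not necessarily |
| Itching | within 1 hour | occurrence yes, resolution not necessarily |
| Skin darkening | about a week or weeks (the wording is garbled) | course not captured |

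One of the four effects outlasts an hour. Its course, and any effect with delayed onset, falls outside the only form described.

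**3. Whether visit 2 has room.** The recall test takes at most 40 × (8 + 1) = 360 s = 6 minutes, against about 10 minutes allotted. That leaves about 4 minutes for arrival and anything else, so a short question fits or nearly fits.

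**4. How much it could show.** Input: 40 participants enrolled. The allocation ratio is not stated. With four equal groups (an assumption), two of which have real current, 2 × 10 = 20 receive it. The 40 are counted at consent, and withdrawal and loss to follow-up are foreseen, so 18 and 16 are shown as illustrations of fewer returning.

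One-sided 95% upper limit for zero events in n: 1 − 0.05^(1/n).

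- n = 20: 1 − 0.05^(1/20) = 13.9%
- n = 18: 15.3%
- n = 16: 17.1%

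Chance of at least one event in 20: 1 − (1 − p)^20. The protocol gives no rate for skin damage, so p is assumed.

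| True rate p | Chance of at least one event in 20 |
|---|---|
| 0.1% | 2% |
| 1% | 18% |
| 2% | 33% |
| 5% | 64% |

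A truly rare effect would probably not appear at all. The question is more useful for effects that are not rare but were not foreseen, and for following up a skin change if one does occur.

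**The case against.** The strongest case against is that this is a design choice with no contradiction behind it. Both aims concern memory, no safety endpoint is stated, and one form after a single session in healthy adults is defensible. The one long-lasting effect is called very rare, a few millimetres in size and harmless. Twenty people will say almost nothing about its rate. If darkening clears in about a week, a check at one week may come too late to see it. Most of this stands, and it is why the point is of low severity. The last argument is weaker, because a question about the whole interval since visit 1 also covers a change that has already cleared.

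A reader might infer more than the documents support:

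- *That several listed effects outlast the session by up to a week.* Redness and itching have an hour as their upper limit and dizziness lasts seconds. Only the skin darkening lasts longer.
- *That later harm is lost.* The consent check implies that participants are told how to report symptoms, reasons for termination are documented, and the consent pages are not available here. The documents support only that harm is not systematically solicited.
- *That the gap is specific to real current.* The schedule is the same in all four groups.
- *That visit 2 would give complete data.* Return is planned, but the protocol foresees withdrawal and loss to follow-up.
- *That the trial would falsely confirm its statement of minimal risk.* That statement is a prior assessment in the risk section. Nothing says that this trial's data will be used to confirm it.

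The content of the visit 1 form is also unknown. If it does not cover side effects, the gap is wider, but that cannot be claimed from what is shown.

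**Conclusion.** The point holds in a narrow form. As described, the protocol has one form after stimulation at visit 1 and no harm question at visit 2. The course of the very rare skin darkening, and any delayed effect, is therefore not systematically collected in any group. This changes no memory result and contradicts no other part of the plan.

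The size is small. Under equal allocation, zero events among about 20 on real current would bound the rate only below about 14%, or about 17% if 16 return. A second question would therefore not establish safety. It would give a like-for-like real-versus-sham record over the week at almost no cost. Severity is low. The conclusion assumes that no harm question is hidden in attachments or consent pages that were not available.

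**What to change.** Add one sentence to the visit 2 description: after the recall test is finished, every participant is asked the same short question on any symptoms, or any skin change at the electrode sites, since visit 1, and the answer is recorded. Asking after recall leaves the memory outcome untouched. State that answers at both time points are reported by real and sham, with the number asked at each.

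An item on when redness or itching stopped is not worth adding at one week, because recall of an effect lasting an hour or less would be unreliable by then. If the visit 1 form already covers side effects, its wording can be reused. If not, a short question has to be written.

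The cost is a one-sentence amendment and one or two more minutes at visit 2. Any report should give the upper limit for zero events, about 14% with 20 participants, so that an absence of events is not over-read.
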